9.5 Study size

The proposed sample sizes in each of the three study groups are as follows:

- 200 women exposed to benralizumab at any time 8 weeks prior to LMP and throughout pregnancy
- 300 women with treated asthma, unexposed to benralizumab, aiming to represent the full spectrum of asthma severity with emphasis on severe patients
- 300 non-asthmatic comparison women

The sample size is considered plausible based on the experience of the OTIS research group with previous studies of asthma in pregnancy, but enrollment rates for the current study are unknown. Although it is unknown to what extent benralizumab will be used by pregnant women, experience with recruitment in the omalizumab (Xolair) EXPECT registry provides some support for the proposed sample size. In six years of recruitment, the EXPECT registry recruited 191 exposed pregnancies ([J. Namazy et al., 2015](#)).

No formal statistical hypothesis testing will be done. Point estimates of the rate ratios and associated CI's between the benralizumab exposed cohort and the unexposed cohorts will be used to evaluate the potential risk of benralizumab to mothers and fetuses.

Table 5 is included to contextualize the magnitude of reported relative risks. This outlines the probability of observing rate ratios in excess of different thresholds either by chance (i.e., when the true underlying risk ratio is 1) or when there is a true underlying increase in risk (RR of 1.2, 1.5 or 2), given the planned sample size.

- If the truth is that there is no increase in risk (true RR=1), the current study would have a relatively small probability (<20%) of reporting out an observed relative risk of 1.5 or greater.
- If the truth is that there is a doubling of risk, the current study would have a higher probability of reporting an observed RR greater than 1.5 ($\geq 70\%$), and a smaller probability of reporting out an observed RR < 1.2 ($\leq 13\%$).

Table 5 Probability that observed relative risk point estimates (exposed/unexposed) will exceed different thresholds

Outcome	Prevalence in unexposed cohort	Expected number of Exposed/ Unexposed Asthmatic cohorts		True RR	Probability observed RR exceeds X			
		enrolled	with complete outcome		X=1.2	X=1.5	X=2.0	X=3.0
All major birth defects in live born infants	3%	200/300	180/270	1	0.38	0.19	0.10	0.02
				1.2	0.51	0.29	0.16	0.04
				1.5	0.68	0.45	0.27	0.08
				2	0.87	0.70	0.49	0.18
Preterm birth	7%	200/300	180/270	1	0.30	0.10	0.02	0.00
				1.2	0.50	0.22	0.06	0.00

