				1.5	0.76	0.47	0.18	0.02
				2	0.96	0.83	0.49	0.08
SGA infant	10%	200/300	180/270	1	0.26	0.07	0.01	0.00
				1.2	0.49	0.19	0.03	0.00
				1.5	0.81	0.48	0.13	0.00
				2	0.99	0.88	0.50	0.05

Numbers in Table 5 are based on 90% of enrolled pregnancies ending in live birth with completed outcome. The effect size for all birth defects among live births is based on a prevalence of 3% in the asthmatic comparison group. The effect size for preterm birth is

based on a prevalence of 7% in the asthmatic comparison group (Bakhireva, 2008). The effect size for small for gestational age infants (SGA) is based on a prevalence of 10% in the asthmatic comparison group. Simulations were done using R to estimate the probabilities presented in Table 5.

It is projected, based on experience with the EXPECT registry that almost all benralizumab-exposed participants will have received at least one dose of the medication in the period of time from eight weeks prior to LMP to the end of the trimester and will be eligible for analysis of major structural birth defects. It is also expected that the majority of study participants will enroll in the study upon recognition of pregnancy in the first trimester; however, some will enroll after 20 weeks' gestation and therefore will not be included in the analysis of spontaneous abortion.

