Elective Termination: The proportion of pregnancies ending in elective termination will be compared between the benralizumab exposed group enrolled prior to 20.0 weeks' gestation, and the diseased and non-diseased cohorts enrolled prior to 20.0 weeks' gestation.

Small for Age Postnatal Growth: After exclusion of twins or higher order multiples, the proportion of pregnancies ending in a live born infant \leq 10th centile of postnatal weight, length and/or head circumference will be compared between the benralizumab group exposed anytime in pregnancy and the treated diseased and non-diseased cohorts.

Statistical methods:

Descriptive tables will be prepared for characteristics of each of the cohorts in each interim and final report displaying n, means, standard deviations, minimums and maximums or proportions and percentages.

For the primary endpoint of major structural defects, and for the secondary endpoints of small for gestational age infants, postnatal growth and elective termination, un-adjusted relative risk estimates will be presented together with exact two-sided 95% and 80% confidence intervals.

For the secondary endpoints of preterm delivery, spontaneous abortion, and stillbirth, survival methods will be used (Kaplan Meier) to estimate crude rates and confidence intervals accounting for gestational timing of enrollment in the study.

Adjusted analyses producing relative risks and 95% and 80% confidence intervals or hazard ratios and 95% and 80% confidence intervals, where numbers permit, will be conducted. A minimum of 30 events in the overall analysis sample is required for adjusted analysis for those outcomes assessed with logistic regression. A minimum of 20 events in the overall analysis sample is required for adjusted analysis for those outcomes assessed with Cox Proportional Hazards.

Confounders will be considered for each adjusted analysis separately, using the method of change in estimate of the effect of exposure to benralizumab by 10% or more. If one confounder is identified, direct adjustment will be performed. However, given the expected low frequency of events in a study of this size, if two or more confounders are identified in any given analysis, a propensity score approach for adjustment will be considered. Appropriateness of models will be assessed graphically and by standard statistical methods.

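### Section 9.7.1 promises adjusted relative risks but names logistic regression as the model, with no step that yields a relative risk

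*Protocol*

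**What the plan says.** All of this stands in Protocol section 9.7.1, under the statistical methods.

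- Crude estimates for major structural defects, SGA, postnatal growth and elective termination: "un-adjusted relative risk estimates will be presented together with exact two-sided 95% and 80% confidence intervals".
- Adjusted estimates: "Adjusted analyses producing relative risks and 95% and 80% confidence intervals or hazard ratios", where numbers permit.
- Event minimum: "A minimum of 30 events in the overall analysis sample is required for adjusted analysis", and this applies "for those outcomes assessed with logistic regression". A separate minimum of 20 events applies to outcomes analysed with Cox models.
- Confounder selection: "using the method of change in estimate of the effect of exposure to benralizumab by 10% or more". Section 9.7.3 adds that the candidate covariate enters a model that already contains exposure.

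Section 9.5 supplies the prevalences in the asthmatic comparison group, 10% for SGA and 3% for major defects among live births. It also says that there will be no formal testing, and that rate ratios with their intervals will be used to evaluate risk.

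**The concern.** Two adjusted effect measures are promised and two models are named. The hazard ratio belongs to the Cox model, which leaves the relative risk to logistic regression. The exposure coefficient of a logistic model is a log odds ratio. The protocol mentions neither an odds ratio nor any device for getting from the logistic fit to a relative risk, so the stated measure and the stated model do not meet.

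If the coefficient is simply exponentiated and reported, the crude and adjusted columns for the same outcome are on different scales. A reader could take the difference between them for confounding. The study relies on point estimates and intervals instead of tests, so the scale of the point estimate is part of the evidence. The logistic model will also be used mainly where the OR and RR differ, because the event minimum lets the common outcomes through and holds the rare ones back.

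**Working it through.** **Inputs (Protocol sections 9.5 and 9.7.1).** Evaluable pregnancies are 90% of 200 and 300, that is 180 and 270. Baseline prevalence p0 is 0.10 for SGA ("small for gestational age infants (SGA) is based on a prevalence of 10"%) and 0.03 for major defects ("birth defects among live births is based on a prevalence of 3"%). The true RRs are those of Table 5: "when there is a true underlying increase in risk (RR of 1.2, 1.5 or 2"), together with 1. The event minimum is 30. No prevalence is given for postnatal growth or elective termination.

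**1. Reproducing the protocol's own figure.** Take two independent binomials, 180 at p0 × RR and 270 at p0, and enumerate exactly the probability that the observed RR exceeds X. For SGA at true RR 2 and X = 1.2, 1.5, 2.0, 3.0 this gives 0.985, 0.878, 0.495, 0.047. Table 5 states 0.99, 0.88, 0.50, 0.05. All SGA and preterm rows agree within 0.01. In the 3% rows the cells at X = 1.2 depend on how ties at exactly 1.2 are counted, which is not an error. Table 5 therefore describes an unadjusted observed RR.

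**2. Which outcomes would be adjusted.** Expected events = 180 × p0 × RR + 270 × p0.

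- SGA: 18 + 27 = 45 at RR 1, and 36 + 27 = 63 at RR 2. The chance of at least 30 events is 0.995 or more. Excluding multiples lowers the counts a little.
- Major defects: 5.4 + 8.1 = 13.5 at RR 1, and 10.8 + 8.1 = 18.9 at RR 2. The chance of at least 30 is below 0.01. If the analysis sample is taken to include all three cohorts, with 3% assumed in the non-asthmatic cohort as well, expected events are 21.6 to 27.0 and the chance is 0.05 to 0.30.

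**3. Size of the gap without confounding.** With p1 = RR × p0, OR = [p1/(1 − p1)] / [p0/(1 − p0)]. For example, at p0 = 0.10 and RR 2, OR = (0.20/0.80)/(0.10/0.90) = 0.25/0.1111 = 2.25.

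| Baseline p0 | RR 1.2 | RR 1.5 | RR 2 |
|---|---|---|---|
| 3% (defects, protocol) | 1.21 (+0.6%) | 1.52 (+1.6%) | 2.06 (+3.2%) |
| 10% (SGA, protocol) | 1.23 (+2.3%) | 1.59 (+5.9%) | 2.25 (+12.5%) |
| 20% (assumed) | 1.26 (+5.3%) | 1.71 (+14.3%) | 2.67 (+33.3%) |
| 25% (assumed) | 1.29 (+7.1%) | 1.80 (+20.0%) | 3.00 (+50.0%) |

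The last two rows are assumptions. They cover the possibility that defining SGA, or small postnatal size, by any one of three measurements at or below the 10th centile lifts the baseline above 10%. At RR 1, OR = RR = 1. Below 1 the OR lies further from 1 in the other direction.

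**4. Reading an OR against Table 5.** Repeating step 1 for SGA at 10% with the observed OR in place of the observed RR, the probability of exceeding 2.0 moves from 0.50 to 0.67 at true RR 2, and from 0.13 to 0.22 at true RR 1.5. At true RR 1 the probability of exceeding 1.5 moves from 0.07 to 0.10, because the OR is also more spread out.

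**5. The 10% screen.** An OR can shift when a covariate unrelated to exposure is added (non-collapsibility). Take a binary covariate independent of exposure, with an assumed prevalence of 30% or 50% and an assumed outcome OR of 2, 3 or 5. At 10% baseline the shift is at most 3.7% for RR 1.5 and 7.5% for RR 2, so the 10% limit is not reached. At an assumed 20% baseline with RR 2 and outcome OR 5 the shift is 13% to 14%.

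**The case against.** The strongest reply is that the protocol fixes the adjusted measure as a relative risk and never says that an OR will be reported. Logistic regression appears once, in a rule about event counts. A logistic fit can deliver an RR by marginal standardisation, and the statistical analysis plan, which is not at hand, may say so. With two or more confounders a propensity score approach will be considered, so the adjustment method is not wholly closed. This stands as far as it goes. A reader might infer that the adjusted results will be odds ratios, but the document does not say so; the distortion arises only if the coefficient is reported as it is. What remains is that the protocol itself names both the measure and the model, and does not connect them.

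A reader might also infer that the 10% screen would flag confounders merely through the move from RR to OR. Section 9.7.3 does not support that: it compares the same model with and without the covariate, so both estimates are on one scale. Non-collapsibility is real but small at the protocol's prevalence (step 5), and is only a minor supporting point.

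A third stronger reading treats Table 5 as a decision rule that an OR would trip. Section 9.5 offers the table as context, it was built from unadjusted proportions, and its natural counterpart is the crude RR, which will be reported in any case. Postnatal growth and elective termination are not in it.

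Last, precision is low. For SGA at 180/270, 10% baseline and RR 1.5 (27 and 27 expected events), the standard error of log RR is √(1/27 − 1/180 + 1/27 − 1/270) = 0.255, giving an approximate 95% interval of 0.91 to 2.47. A 6% shift of scale is small beside that. It is nevertheless systematic for any true effect, and can be avoided at almost no cost.

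**Conclusion.** The concern holds as a mismatch between the adjusted measure that section 9.7.1 promises and the model that it names, with consequences for secondary outcomes. SGA is the clear case, because its adjusted analysis is almost certain to run. At the protocol's own 10% prevalence, an unconverted coefficient would overstate an RR of 1.2 to 2 by 2% to 12.5%. Larger gaps, such as 33% at RR 2, need a baseline of about 20%, which is an assumption for the SGA composite and for postnatal growth; for elective termination no baseline is stated and the gap cannot be sized. There is no shift at RR 1, so the scale itself does not create an effect where none exists. The primary outcome is essentially untouched: about 3% at RR 2, and seldom enough events for adjustment. The sizes in the table assume no confounding. They apply only if no standardisation or conversion is carried out, and the protocol neither states nor rules out such a step.

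**What to change.** In section 9.7.1, state that adjusted RRs for SGA, postnatal growth, elective termination and, if adjusted at all, major defects come from one of two routes:

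- modified Poisson regression (log link) with robust variance; or
- logistic regression followed by marginal standardisation to an RR, with bootstrap 95% and 80% intervals.

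Reword the event-minimum sentence to match the chosen model and keep the minimum at 30. State that the 10% change-in-estimate rule is evaluated on the same RR scale. Either route removes the mismatch, and the choice between them is a matter of preference. Should the investigators prefer to keep plain logistic output, the lesser remedy is to label it as an odds ratio and show a crude odds ratio beside it, which means giving up the promised adjusted RR.

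The cost is a few words and one model statement in the code, with no change to design, data collection or sample size. Modified Poisson is slightly less efficient than maximum likelihood, and a small-sample correction to the robust variance is advisable when events are near 30.

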9.7.2 Exploratory/sensitivity analyses

Exploratory analyses addressing potential effect modifiers such as Asthma Control Test measures of disease symptom control, and measures of asthma exacerbation will be addressed.

In addition, sub-analyses based on length and gestational timing as well as dose of exposure to benralizumab will be performed.

Stratified analyses based on prenatal diagnostic test performed prior to enrollment in the study will be conducted for the primary endpoint. The purpose of this analysis is to address the inherent bias in excluding women at the time of enrollment in the cohort study who have already received prenatal diagnosis of a major structural birth defects, but including women who have already had a normal result or prenatal diagnosis for major structural birth defects prior to enrollment. Therefore, the planned stratified analysis will compare the birth prevalence of major structural birth defects among the subset of women enrolled in the cohorts prior to prenatal diagnostic testing to detect structural defects (ultrasound for structure, chorionic villus sampling, amniocentesis), to the birth prevalence of major birth defects among the subset of women enrolled in the cohorts after prenatal diagnostic testing to detect structural defects.

Regarding asthma severity, the measures are only captured after enrollment, and in the exposed group only after being on treatment, so they would typically not be included in the analysis as adjustment factors as they could be mediators. However, descriptive analyses of the balance in cohorts on measures of disease severity are presented. Sub-analyses or

sensitivity analyses within disease severity categories can be performed, depending on the distribution of the covariates. This would be described in detail in the SAP.

Sub-analyses excluding chromosomal or known genetic anomalies (classified by study investigators as having a known genetic etiology) will also be conducted. Details will be provided in the SAP.

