9.2 Setting

The study population consists of three cohorts of pregnant women (See Section 9.5 for sample size).

Participants will be recruited into the three cohorts concurrently, on the basis of the following inclusion/exclusion criteria:

Cohort 1: Benralizumab-Exposed

Inclusion Criteria:

- Currently pregnant women diagnosed with asthma who contact the OTIS Research Center and who have been exposed to benralizumab for any number of days, at any dose, and at

any time from 8 weeks before the first day of LMP up to and including the end of pregnancy.

- Eligible participants will be currently pregnant women who agree to the conditions and requirements of the study including the interview schedule and release of medical records.

Exclusion Criteria:

- Women who have had exposure to another biologic, used for any indication, anytime during pregnancy or within 8 weeks of LMP.
- Women will not be eligible for Cohort 1 if they first contact the OTIS Research Center after prenatal diagnosis of a major structural birth defect.
- Retrospective cases (outcome of pregnancy known prior to enrollment).
- Women who have enrolled in the current study with a previous pregnancy.

Cohort 2: Treated Diseased Comparison

Inclusion Criteria:

- Currently pregnant women diagnosed with asthma and exposed to asthma medications for any number of days, at any dose, and at any time from LMP up to the date of enrollment, who contact the OTIS Research Center but who were not exposed to benralizumab during pregnancy or within 8 weeks prior to LMP.
- Eligible participants will be currently pregnant women who agree to the conditions and requirements of the study including the interview schedule and release of medical records.

Exclusion Criteria:

- Women with exposure to benralizumab any time during pregnancy or within 8 weeks prior to LMP.
- Women will not be eligible for Cohort 2 if they first come in contact with the OTIS Research Center after prenatal diagnosis of a major structural birth defect.
- Retrospective cases (outcome of pregnancy known prior to enrollment).
- Women who have enrolled in the current study with a previous pregnancy.

Cohort 3: Non-Asthmatic Comparison

Inclusion Criteria:

- Currently pregnant women who contact the OTIS Research Center.
- Eligible women may potentially have been exposed to non-teratogenic agents during this pregnancy.

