9.7 Statistical analysis

9.7.1 Main analysis

A detailed Statistical Analysis Plan (SAP) will be prepared and finalized prior to the submission of the first interim report.

Primary Endpoint:

The primary endpoint will be major structural defects among live born infants.

The primary comparison will be between the first-trimester benralizumab-exposed group and the disease cohort receiving asthma treatment anytime in pregnancy.

Secondary comparisons for major structural birth defects will be conducted within the subgroup of pregnancies ending in live birth, spontaneous abortion, stillbirth or elective termination, excluding lost-to-follow-up, comparing first-trimester benralizumab-exposed to the treated disease cohort.

Additional secondary comparisons will be made between the first-trimester benralizumab-exposed group and the treated asthma and non-asthmatic cohort, and between the treated asthma and non-asthmatic cohorts. Further details will be specified in the SAP.

Secondary Endpoints:

Preterm Delivery: After exclusion of twins or higher order multiples, the proportion of pregnancies ending in live birth <37 weeks' gestation will be compared between the benralizumab group enrolled and exposed anytime in pregnancy prior to 37.0 weeks' gestation and the treated diseased and non-diseased cohorts enrolled prior to 37.0 weeks' gestation.

Small for Gestational Age Infants: After exclusion of twins or higher order multiples, the proportion of pregnancies ending in a live born infant \leq 10th centile of birth weight, length and/or head circumference will be compared between the benralizumab group exposed anytime in pregnancy and the treated diseased and non-diseased cohorts.

Spontaneous Abortion: For those women in all three cohorts who enrolled in the study prior to 20.0 weeks' gestation, the proportion of pregnancies ending in spontaneous abortion accounting for left truncation will be compared between those in the benralizumab group enrolled and exposed any time in pregnancy prior to 20.0 weeks' gestation and those in the treated diseased and non-diseased cohorts.

Stillbirth: The proportion of pregnancies ending in stillbirth will be compared between those in the benralizumab-exposed group and those in the treated diseased and non-diseased cohorts.

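### The prenatal-testing analysis contrasts women enrolled before and after testing, so it gives no benralizumab-versus-treated-asthma RR free of the enrollment selection

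*Protocol*

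**What the plan says.** All three cohorts exclude women whose first contact follows a prenatal diagnosis (Protocol 9.2). For the exposed cohort: "Women will not be eligible for Cohort 1 if they first contact the OTIS Research Center after prenatal diagnosis of a major structural birth defect". Women who have already had a normal test remain eligible.

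Section 9.7.2 responds to this: "Stratified analyses based on prenatal diagnostic test performed prior to enrollment in the study will be conducted for the primary endpoint". Its reason is given next: "The purpose of this analysis is to address the inherent bias in excluding women at the time of enrollment in the cohort study" while admitting those with a normal result. It then fixes the contrast. The analysis will "compare the birth prevalence of major structural birth defects among the subset of women enrolled in the cohorts prior to prenatal diagnostic testing" for structural defects, "to the birth prevalence of major birth defects among the subset of women enrolled in the cohorts after prenatal diagnostic testing to detect structural defects". Unlike the paragraphs of 9.7.2 on asthma severity and on genetic anomalies, this one leaves nothing to the SAP.

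The comparison to be protected is in 9.7.1: "The primary comparison will be between the first-trimester benralizumab-exposed group and the disease cohort receiving asthma treatment anytime in pregnancy".

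Section 9.3.3 lists prenatal tests, their timing and their results among the potential confounders. Section 9.7.1 requires at least 30 events before an outcome analyzed by logistic regression is adjusted.

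**The concern.** The study's main result is a ratio of defect prevalence between exposed and treated-asthma pregnancies. The exclusion rule lowers the observed prevalence among women who enroll after testing. If both cohorts have the same share of such women and the same detection, the ratio is hardly affected. If the shares differ, the crude RR moves away from the truth in a direction set by which cohort enrolls later.

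The planned contrast sets early enrollees against late enrollees. Drug exposure defines neither side, so the result cannot show whether the benralizumab RR is distorted, and it offers no RR to put beside the crude one. The study does no hypothesis testing and will be read from its point estimates and intervals, so a reader would have nothing with which to judge this bias.

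**Working it through.** **Inputs from the Protocol.** Section 9.5 and Table 5 give 3% defect prevalence in the asthmatic comparison group and 180 exposed and 270 comparator pregnancies with complete outcome. Section 9.7.1 gives the 30-event minimum.

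**Inputs assumed.** The documents give neither the share of defects detected before enrollment (s, taken as 0.3 to 0.7) nor the share of each cohort enrolled after testing (f₁ exposed, f₀ comparator). The 3% is taken to apply before testing.

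**Check of the plan's own figure.** Exact enumeration of two binomials (180 and 270; 3% in comparators) gives P(observed RR > 1.5) = 0.187 at true RR 1 and 0.698 at true RR 2. Table 5 states 0.19 and 0.70, so the inputs are read correctly. The prenatal-testing analysis has no stated figure.

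**Step 1: effect of the exclusion.** Prevalence after a normal test = p(1 − s)/(1 − ps). With p = 0.03 and s = 0.5: 0.015/0.985 = 0.0152. The before/after ratio is 0.0300/0.0152 = 1.97.

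**Step 2: crude RR with no drug effect.** Cohort prevalence = (1 − f) × 0.0300 + f × 0.0152. For f₁ = 60% and f₀ = 30%, this is 0.0211 and 0.0256, so the crude RR is 0.83.

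| Enrolled after testing, exposed / comparator | Planned before/after ratio | Crude RR | RR within each stratum |
|---|---|---|---|
| 50% / 50% | 1.97 | 1.00 | 1.00 |
| 60% / 30% | 1.97 | 0.83 | 1.00 |
| 30% / 60% | 1.97 | 1.21 | 1.00 |
| 40% / 20% | 1.97 | 0.89 | 1.00 |
| 20% / 40% | 1.97 | 1.12 | 1.00 |

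The planned ratio is the same in every row while the crude RR moves. Over s = 0.3 to 0.7, the 60/30 split and its reverse give crude RRs between 0.74 and 1.36.

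**Step 3: true RR 2, s = 0.5.** With equal timing the before/after ratio is 1.95, against 1.97 at RR 1. With 60/30 timing and cohorts pooled it is 1.58, and 2.41 reversed, so it mixes drug effect with timing. The within-stratum RRs are 2.00 and 2.03; pooled by Mantel-Haenszel, about 2.01.

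**Step 4: the adjusted route.** Expected cases in the asthma cohorts at RR 1: 0.03 × (180 + 270) = 13.5. At RR 2: 0.06 × 180 + 0.03 × 270 = 18.9. Adding 270 non-asthmatic pregnancies at an assumed 3% (8.1 cases) gives 21.6 and 27.0. All are below 30.

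**Step 5: limit of pooling.** Let 40% of each cohort enroll late, with detection of 60% in exposed and 40% in comparators and no drug effect. After-test prevalences are 0.0122 and 0.0182. The pooled RR is (0.6 × 0.0300 + 0.4 × 0.0122)/(0.6 × 0.0300 + 0.4 × 0.0182), about 0.91. At 70% against 30% detection it is 0.82. The before-testing RR is 1.00 in both.

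**Step 6: precision.** At RR 1, 5.4 and 8.1 cases give SE(log RR) = √(1/5.4 − 1/180 + 1/8.1 − 1/270) = 0.55. With half of each cohort per stratum (90 and 135; 2.7 and 4.05 cases) it is √(1/2.7 − 1/90 + 1/4.05 − 1/135) = 0.77. P(observed RR > 1.5) in such a stratum is 0.23 at RR 1 and 0.61 at RR 2.

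**The case against.** - **The contrast has a use.** Section 9.1 says the design yields absolute as well as relative risks, and the before/after difference measures how far prior testing lowers absolute prevalence. This stands. A reader might infer that the analysis is worthless against the bias it names; that is too strong. Eligibility suggests the direction of the difference, but not its size.
- **It is not the only safeguard.** A reader might infer that nothing else guards against this bias. Section 9.3.3 lists prenatal testing as a candidate confounder, the exclusion applies to all three cohorts, recruitment is concurrent, and comparators are similarly ascertained. This also stands, although Step 4 shows the adjusted route is unlikely to open.
- **A by-cohort reading is possible.** The paragraph speaks of stratified analyses and of cohorts in the plural. If prevalences were shown by cohort and stratum, within-stratum RRs would follow by division. But the sentence that fixes the contrast does not say so.
- **The illustration may be harsh.** Section 9.5 expects most women to enroll in the first trimester, which fits poorly with 60% enrolling after testing. At 40/20 the log-RR shift is about 0.12, roughly one fifth of the standard error of 0.55. This limits the weight of the point.
- **It is exploratory, and a SAP may add detail.** True, and choice of pooling method is normal SAP content. The contrast, however, is fixed in the Protocol without deferral.

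**Conclusion.** The point holds in a limited form. As written, the analysis describes depletion of defects by prior testing and provides no benralizumab-versus-treated-asthma RR free of that selection. It therefore does not protect the primary comparison if enrollment timing differs between cohorts.

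With 50% detection and no drug effect, the crude RR would be 0.83 or 1.21 at 60/30 late enrollment, and 0.89 or 1.12 at 40/20. These rest on assumed shares; the documents do not show that timing will differ, so they do not support a claim that the primary RR is biased by any given amount. Nor should stratification be read as a complete cure: the pooled RR is free of this bias only if prenatal detection is similar across cohorts.

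The weight is moderate. The analysis is exploratory and random error will exceed the likely bias, but the correction is simple and should be made.

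**What to change.** Replace the sentence in 9.7.2 that fixes the contrast with text to this effect:

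*The RR of major structural defects for first-trimester benralizumab versus treated asthma, with 95% and 80% confidence intervals, will be estimated separately in women enrolled before and after prenatal diagnostic testing. The before-testing estimate is the key sensitivity result, because the enrollment exclusion does not act on it. A Mantel-Haenszel RR pooled over the two strata will be shown beside the crude RR; it assumes similar prenatal detection in the two cohorts.*

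Add a table of the share enrolled after testing by cohort. Keep the before/after contrast, labeled descriptive.

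The cost is one sentence and one table, from test dates and results already collected. The downside is precision: with about 2.7 and 4 cases in a half-sized stratum, the intervals will be wide and a stratum may have no cases in one cohort. The stratum results should be read as a check on the crude RR rather than as a replacement for it.
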